### **8.2.1 Duration of the study**

There is no set duration of participation. Patients can remain in the safety sub-registry as long as they receive Cerezyme or Cerdelga and the sub-registry is open. The number of patients for both of the groups who continue their observation in the safety sub-registry will be evaluated annually after the end of the recruitment period to determine the need to replace patients who dropped out of the study for any reason. The need to continue with this requirement will be reassessed two years after the last Cerdelga patient has been enrolled in the study in the interim report.

Data collection will be concluded four years after the last Cerdelga patient has been enrolled in the study, at which time analysis will be performed.

### **8.2.2 Eligibility criteria**

#### **8.2.2.1 Inclusion criteria**

Patients must meet the following criteria to be eligible to participate in the safety sub-registry:

- I 01. Male or female patient aged 18 years or older;
- I 02. The patient must be enrolled in the ICGG Gaucher Registry prior to safety sub-registry enrollment;
- I 03. The patient is willing and able to provide written informed consent for the safety sub-registry;
- I 04. The patient must have a confirmed diagnosis of GD, as defined in the protocol of the ICGG Gaucher Registry (documented acid  $\beta$ -glucosidase deficiency and/or mutations in the acid  $\beta$ -glucosidase gene);
- I 05. The patient must either initiate or continue treatment with Cerdelga or Cerezyme at the time of safety sub-registry enrollment.

#### **8.2.2.2 Exclusion criteria**

A patient who meets any of the following criteria will be excluded from this sub-registry:

- E 01. The patient is concurrently enrolled in another clinical study; or participates in the compassionate use program with Cerdelga.
- E 02. The patient is treated with both Cerezyme and Cerdelga at the time of enrollment, or investigator consider treating patient with both therapies concurrently at any time during participation in the safety sub-registry.

### **8.2.3 Analysis population(s)**

Analysis will be performed on the Safety Set, defined as all patients enrolled in the sub-registry who have received at least one dose of Cerdelga or Cerezyme following enrollment.

Category of treatment status at the time of sub-registry enrollment will be defined as:

- a) Patients naive to any GD treatment (ERT or SRT). This category will include, for example, newly diagnosed patients.
- b) Patients naive to the product of interest (Cerdelga in the Cerdelga group and Cerezyme in the comparator group) but experienced to any other treatment for GD (ERT or SRT). This category will include, for example, patients who will switch from any one therapy to the product of interest.
- c) Patients experienced to the treatment of interest. This category will include patients who were on treatment with the product of interest at entry into the sub-registry and then continue this therapy.

Note:

- Patients whose first GD treatment is commercial Cerdelga or Cerezyme, and who enroll in the sub-registry within 3 months of the first dose will be considered treatment naive for the purposes of analysis. Regardless of prior treatment, these patients must receive either Cerdelga or Cerezyme during their participation in the sub-registry.
- Previous exposure to Cerdelga in clinical studies will be considered for any patient of the sub-registry, notwithstanding the group of treatment they belong to during sub-registry participation.
- The data for enrolled patients who switch treatment from Cerdelga to Cerezyme or vice-versa during follow-up will be evaluated to and from the point of switch in the therapy (if applicable).
- A subset of treatment experienced patients will be patients who will switch from any one therapy to any other therapy.
- When available, AEs reported by the patient and in the opinion of investigator related to Cerdelga intake and Cerezyme administration (prior to enrollment into the safety sub-registry) will be collected as part of the patient enrollment characteristics (medical history).

Analysis of endpoint: The main analysis of interest will be the incidence rate of any AE report for Cerdelga-treated patients during their participation in the sub-registry, considering treatment status at sub-registry enrollment (if applicable). Similar calculations will be performed for the Cerezyme-treated patients. Summaries will also be presented for three categories of treatment status within each of the Cerdelga and Cerezyme groups (if applicable). Data will be analyzed as available, missing data will not be imputed. All summaries will be descriptive; no formal hypothesis testing will be performed.

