## 8 RESEARCH METHODS

### 8.1 STUDY DESIGN

This is a safety sub-registry of the ICGG Gaucher Registry (DIREGC07009).

This is a non-interventional, multicenter, prospective PASS of Cerdelga, a treatment approved in many countries for adult patients with GD1 who have a CYP2D6 PM, IM, or EM phenotype. Participating HCPs will enroll eligible patients after the decision to treat with Cerdelga or Cerezyme. The study will enroll patients who will be receiving Cerdelga or Cerezyme for the first time or as part of ongoing treatment of their GD.

Patients will receive treatment as determined by the patient's HCP and guided by the provisions of the prevailing locally approved product labelling and educational materials, and the ICGG Gaucher Registry recommendations for monitoring. All treatment decisions and medical assessments are at the discretion of the HCPs and are not mandated by study design or protocol.

No experimental intervention is involved. Participating patients will undergo clinical assessments and receive the standard of-care treatment for GD, as determined by their treating HCPs, who may want to use the Gaucher registry Recommended Schedule of Assessments as a guideline. The observational nature of this study design will allow for an estimate of 'real world' safety experience of Cerdelga among patients who receive Cerdelga in a commercial versus clinical study setting.

Patients will complete and sign a patient written Informed Consent Form specific to this safety sub-registry before participating.

Selected data from the sub-registry CRFs will be monitored periodically against source documents at the treating HCP's site by a representative of Sanofi Genzyme (or its designee) to ensure data completeness and accuracy. Refer to [Section 8.7.2](#) for further details.

Study baseline will be defined as the time of entry into the sub-registry.

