### **8.3 VARIABLES**

The main analysis of interest will be the incidence rate of any AE report for Cerdelga-treated patients during participation in the sub-registry.

The outcome variable will be a report of an AE, exposure will be duration (in months or years) of time of exposure to Cerdelga while enrolled in the sub-registry, grouping factors will include category of Treatment Status (defined below), duration of GD treatment (including Cerdelga or other GD treatments) prior to enrolling in the sub-registry, selected demographic and baseline characteristics such as age, sex, and genotype as listed in [Section 8.7.5](#).

Category of treatment status at the time of sub-registry enrollment will be defined as:

- a) Patients naive to any GD treatment (ERT or SRT). This category will include, for example, newly diagnosed patients.
- b) Patients naive to the product of interest (Cerdelga in the Cerdelga group and Cerezyme in the comparator group) but experienced to any other treatment for GD (ERT or SRT). This category will include, for example, patients who will switch from any one therapy to the product of interest.
- c) Patients experienced to the treatment of interest. This category will include patients who were on treatment with the product of interest at entry into the sub-registry and then continue this therapy.

Note:

- Patients whose first GD treatment is commercial Cerdelga or Cerezyme, and who enroll in the sub-registry within 3 months of the first dose will be considered treatment naive for the purposes of analysis. Regardless of prior treatment, these patients must receive either Cerdelga or Cerezyme during their participation in the sub-registry.
- Previous exposure to Cerdelga in clinical studies will be considered for any patient of the sub-registry, notwithstanding the group of treatment they belong to during sub-registry participation.
- The data for enrolled patients who switch treatment from the Cerdelga to the Cerezyme or vice-versa during follow-up will be evaluated to and from the point of switch in the therapy.

- A subset of treatment experienced patients will be patients who will switch from any one therapy to any other therapy.
- When available, AEs reported by the patient and in the opinion of investigator related to Cerdelga intake and Cerezyme administration (prior to enrollment into the safety sub-registry) will be collected as part of the patient enrollment characteristics (medical history).

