### **8.10 LIMITATIONS OF THE RESEARCH METHODS**

During the clinical studies the frequency of AEs had a tendency to decrease over time. To control for a possible relation between the frequency of AEs and the duration of treatment, AEs will also be analyzed after stratification of patients between three categories of treatment status.

For the sub-registry to meet its goal of providing real-world information on Cerdelga safety, the design of the study must ensure that HCPs report all AEs without preconceived ideas on the safety profile of Cerdelga. To this end no AESI have been specified.

To determine if there are any differences between patients who accept to enroll in the sub-registry and those who do not and, if these differences have any impact on the generalizability of the results, baseline characteristics (including age, sex, genotype, GD history, GD treatment history, current GD treatment and CYPD phenotype) of patients who were enrolled in the safety sub-registry will be compared based on provisions of ICGG Gaucher registry ICF with baseline characteristics of ICGG Gaucher registry patients who did not accept to enroll into safety sub-registry, if this information can be obtained.

Baseline characteristics of subjects who discontinue the study and subjects who complete the study will be summarized in the clinical study report. In addition, number and percent of subjects who discontinue the study will be provided.

The patients enrolled in the ICGG safety sub-registry are not expected to have an extra burden of physician visits or out of the standard of care procedures/tests to comply with, thus any drop out would be mostly expected for reasons not related to the safety sub-registry or for patients who transfer from either Cerdelga and Cerezyme to another GD treatment.

The number of patients for both of the groups who continue their observation in the safety sub-registry will be evaluated annually after the end of the recruitment period to determine the need to replace patients who dropped out of the study for any reason. The need to continue with this requirement will be reassessed two years after the last Cerdelga patient has been enrolled in the study in the interim report.

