### **10.1.3 Obligations of the Investigator regarding safety reporting**

#### **10.1.3.1 Adverse Events collection**

All AEs regardless of relationship to Cerdelga or Cerezyme, spanning from the signature of the informed consent form until the end of the collection period for each patient (the last follow-up assessment of the particular patient), are to be recorded **immediately** (within 24 hours of awareness) for SAE and within 30 days of awareness for non-serious AE on the corresponding page(s) of the paper CRF or e-CRF, as explained below.

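### Treatment-naive patients may enrol up to 3 months after first dose with that time uncounted, so early incidence should be checked from first dose with delayed entry

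*Combined protocol and SAP*

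**What the plan says.** Section 8.2.3 defines three treatment-status categories at sub-registry enrolment: (a) naive to any Gaucher treatment, (b) naive to the product but treated before, and (c) experienced. A note there, repeated in Sections 8.3 and 8.8, widens category a. It concerns people who began Gaucher therapy with one of the two marketed products, and says that those "who enroll in the sub-registry within 3 months of the first dose will be considered treatment naive for the purposes of analysis".

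Four other provisions decide what is observed for these patients:

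- **Time zero (Section 8.1):** "Study baseline will be defined as the time of entry into the sub-registry".
- **Events (Section 10.1.3.1):** AEs are collected over a period "spanning from the signature of the informed consent form until the end of the collection period for each patient". The main analysis in Section 8.2.3 is the "incidence rate of any AE report for Cerdelga-treated patients during their participation in the sub-registry".
- **Person-time (Section 8.3):** "exposure will be duration (in months or years) of time of exposure to Cerdelga while enrolled in the sub-registry".
- **Events before enrolment (Section 8.2.3):** these are recorded as medical history when available, if the patient reports them and the investigator judges them related. No analysis adds them to the rate.

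Section 8.10 explains the reliance on treatment status: "During the clinical studies the frequency of AEs had a tendency to decrease over time". It uses the three strata to control for that relation. Section 8.8 says that the assumption of a constant incidence rate will be evaluated, but names no time scale or method.

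**The concern.** Two kinds of patient share the naive label. One starts treatment at enrolment and is observed from first dose. The other enrols some weeks after first dose and is left-truncated: time from first dose to consent is unobserved, and the patient enters only if still on a study product, or moved to the other one, at enrolment.

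If AEs are more frequent early in treatment, the second group brings mostly later, quieter time into the stratum nearest to treatment start. Two results are exposed. The early AE rate in naive patients is biased down. A constancy check with time zero at sub-registry entry would also line up the first weeks of treatment in some patients with months 4 to 6 in others, and so flatten a real decline. A finding of no early excess could then come partly from when patients enrolled. If late enrolment were more common on one product, the comparison of the two naive strata would also be affected.

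**Working it through.** **The plan's own figure.** The plan gives no figure on this point. Its one calculable probability (Section 8.6.1: 100 patients, cumulative rate 5%) reproduces as 1 - 0.95^100 = 0.994, consistent with the stated more than 95%. It does not bear on the question.

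**Inputs from the documents.** The window is 3 months (0.25 years). Events and exposure both start at consent or enrolment. Follow-up for the last Cerdelga patient is 4 years (Section 8.2.1).

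**Assumptions, because the documents are silent.** The AE rate is 4 per person-year in months 0-3 of treatment and 2 afterwards (ratio R = 2). All events count, not only the first. Late enrollees have a delay spread uniformly over 0-3 months (mean observed early time 0.125 years) or all enrol at month 3. No loss of early stoppers is modelled.

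**Rate over the first 6 months on drug** = mean events / mean observed person-time:

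- All observed from first dose: (4×0.25 + 2×0.25)/0.5 = 3.00
- Half late, uniform delay: (1.5 + 1.0)/(0.5 + 0.375) = 2.5/0.875 = 2.86
- All late, uniform delay: (4×0.125 + 2×0.25)/0.375 = 1.0/0.375 = 2.67
- All enrolled at month 3: (2×0.25)/0.25 = 2.00

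**Rate over 4 years from enrolment:**

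- All observed from first dose: (4×0.25 + 2×3.75)/4 = 2.125
- All late, uniform delay: (4×0.125 + 2×3.875)/4 = 2.0625
- Half late, uniform delay: (2.125 + 2.0625)/2 = 2.094
- All enrolled at month 3: 2.00

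| Naive patients enrolled | Share of months 0-3 observed | First 6 months on drug | First 3 months after entry | 4 years from entry |
|---|---|---|---|---|
| all at first dose | 100% | 3.00 | 4.0 | 2.125 |
| half late, uniform | 75% | 2.86 (5% low) | 3.5 | 2.094 (1.5% low) |
| all late, uniform | 50% | 2.67 (11% low) | 3.0 | 2.0625 (3% low) |
| all at month 3 | 0% | 2.00 (33% low) | 2.0 | 2.00 (6% low) |

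**Effect on a check run from entry.** The true ratio of early to later rate is 4/2 = 2.0. Measured on time since entry, the ratio of the first 3 months to later time is 3.5/2 = 1.75, 3.0/2 = 1.5 and 2.0/2 = 1.0 in the three late patterns.

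**The same check from first dose with delayed entry.** The rate in months 0-3 is (1.0 + 0.5)/(0.25 + 0.125) = 4.0 with half late, and 0.5/0.125 = 4.0 with all late and uniform delay. The true ratio of 2.0 is recovered. If all enrol at month 3 there is no person-time in that interval, so the analysis shows a gap rather than a false flat line.

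**Range over R.** With R = 1 there is no effect. With R = 4 (8, then 2) and all enrolled late, the 4-year rate is 0.92 (uniform delay) to 0.84 (all at month 3) of the rate with entry at first dose. The rate in the first 3 months after entry is then 0.63 to 0.25 of its true value.

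**The case against.** The strongest reply is that the plan already holds part of the remedy. Section 8.3 and the Abstract list duration of Gaucher treatment before enrolment as a grouping factor, which could separate patients with no prior exposure from those with up to 3 months. This stands in part. No cut-point at zero is given, and grouping by prior duration does not set the time scale of the constancy check.

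It is also fair that the study is descriptive, its aim is long-term safety, no 3- or 6-month rate is planned, and Section 8.8 makes stratum rates conditional on enough data. The label does not itself cause the loss, because collection from consent does. These points limit the importance of the matter. They do not answer the question of time scale, and the check in Section 8.8 can use all patients.

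A reader might infer more than the documents support:

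- *That the naive stratum misses the early period.* It does not. Inclusion criterion I 05 admits patients who initiate at enrolment, and they are observed from first dose. Others lose at most 3 months.
- *That early stoppers never enter.* A patient who stops one product can restart it, or enrol on the other, and a related event may then appear as medical history.
- *That the rate is diluted by immortal time.* Events and exposure before consent drop out together.
- *That the note contradicts category c.* Late enrollees do fit its wording, "patients who were on treatment with the product of interest at entry into the sub-registry and then continue this therapy", but the note states how they are to be treated for analysis and reads as an override.
- *That the strata exist to show early onset.* Section 8.10 says only that they control for duration of treatment, and gives neither the size nor the timing of the decline.

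**Conclusion.** The concern holds in limited form. Among patients labelled naive who enrol after first dose, up to 3 months of early AEs and exposure are uncounted, and they are pooled with patients observed from first dose. If AE frequency falls with time on treatment, the stratum's early rate is biased down, and a check timed from sub-registry entry understates the decline.

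Under the assumed rates of 4 and then 2 per person-year, the 6-month rate is about 5% to 33% low, depending on how many enrol late and how late. The planned rate over about 4 years is only about 1.5% to 6% low. The direction depends on an early excess, which Section 8.10 suggests but does not quantify. The size depends on the share and delay of late enrollees, which the documents do not give. The long-term rate is little affected. The weakness lies in any statement about early onset or constant incidence.

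**What to change.** In Section 8.8:

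1. Run the constant-incidence check on time since first dose of the product, with each patient entering the risk set at the enrolment date.
2. Within the existing grouping by prior treatment duration, set a cut-point at zero. Naive patients enrolled at or before first dose are then shown separately from those enrolled after it, where numbers allow. The 3-month note can stay as a label.
3. Base any statement on early AE onset on person-time actually observed from first dose.

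Delayed entry does not bring back patients who stopped treatment before they could enrol. The split in item 2 gives a view of whether late enrollees differ.

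The cost is a change of analysis wording and one further table split. The treatment start date and the enrolment date are already collected (Section 8.7.5), so no new data or recruitment is needed. The downside is that the subgroup observed from first dose may be small, and its rates will then be imprecise.

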## **8.2.4 Modalities of recruitment**

### **8.2.4.1 Investigator selection**

The sub-registry study patients will be recruited from sites in countries where Cerdelga is already on the market or will become available on the market during the sub-registry enrollment period. Both ICGG Gaucher Registry sites and new sites, which could potentially become ICGG Gaucher

Registry sites, will be considered for the study. Health Care Providers at these sites who manage patients with GD1 will be invited to participate in the sub-registry.

#### **8.2.4.2 Patient selection**

The patients who will be enrolled in the study will be selected among the patients who are enrolled or agree to enroll in the ICGG Gaucher Registry and either initiate or continue treatment with Cerdelga or Cerezyme while enrolled in the sub-registry.

Each participating HCP is solely responsible for determining the appropriate clinical care for each patient. The Investigator/HCP should refer to the locally approved prescribing information for any information on the treatment being administered.

### **8.3 VARIABLES**

The main analysis of interest will be the incidence rate of any AE report for Cerdelga-treated patients during participation in the sub-registry.

The outcome variable will be a report of an AE, exposure will be duration (in months or years) of time of exposure to Cerdelga while enrolled in the sub-registry, grouping factors will include category of Treatment Status (defined below), duration of GD treatment (including Cerdelga or other GD treatments) prior to enrolling in the sub-registry, selected demographic and baseline characteristics such as age, sex, and genotype as listed in [Section 8.7.5](#).

Category of treatment status at the time of sub-registry enrollment will be defined as:

- a) Patients naive to any GD treatment (ERT or SRT). This category will include, for example, newly diagnosed patients.
- b) Patients naive to the product of interest (Cerdelga in the Cerdelga group and Cerezyme in the comparator group) but experienced to any other treatment for GD (ERT or SRT). This category will include, for example, patients who will switch from any one therapy to the product of interest.
- c) Patients experienced to the treatment of interest. This category will include patients who were on treatment with the product of interest at entry into the sub-registry and then continue this therapy.

Note:

- Patients whose first GD treatment is commercial Cerdelga or Cerezyme, and who enroll in the sub-registry within 3 months of the first dose will be considered treatment naive for the purposes of analysis. Regardless of prior treatment, these patients must receive either Cerdelga or Cerezyme during their participation in the sub-registry.
- Previous exposure to Cerdelga in clinical studies will be considered for any patient of the sub-registry, notwithstanding the group of treatment they belong to during sub-registry participation.
- The data for enrolled patients who switch treatment from the Cerdelga to the Cerezyme or vice-versa during follow-up will be evaluated to and from the point of switch in the therapy.

- A subset of treatment experienced patients will be patients who will switch from any one therapy to any other therapy.
- When available, AEs reported by the patient and in the opinion of investigator related to Cerdelga intake and Cerezyme administration (prior to enrollment into the safety sub-registry) will be collected as part of the patient enrollment characteristics (medical history).

Other outcome variables include SAEs, events of interest, reported values of the clinically significant abnormal laboratory result in the course of AE follow-up, and frequencies and percentages of timing of CYP2D6 genotyping, and CYP2D6 predicted phenotypes and GD subtype among Cerdelga-treated patients will be presented.

